	8.5.		
	8.6	ADVERSE EVENT REPORTING	
	8.6.		
	8.6.		
	8.6.	-	
	0.0.	8.6.3.1 FOLLOW-UP INFORMATION	
	8.7	STUDY CLOSE-OUT	
	8.7		
	0.7	8.7.1.1 7 CALENDER DAY TELEPHONE OR FAX REPORT.	
		8.7.1.2 15 CALENDER DAY WRITTEN REPORT	
	8.8	FAX NUMBER FOR IND SAFETY REPORTS.	
	8.9	IN CASE OF EMERGENCY	
	8.10	DATA SAFETY MANAGEMENT PLAN	
	8.11	STUDY OVERSIGHT	_
	8.12	REPORTING CHANGES IN STUDY STATUS	
9	DAT	A QUALITY AND SAFETY REVIEW PLAN AND MONITORING	39
	9.1	DATA QUALITY AND MANAGEMENT	39
	9.1	-	
	9.1		
	9.2	SUBJECT ACCRUAL AND COMPLIANCE	
	9.2		

	9.2	2.2 MEASUREMENT AND REPORTING OF PARTICIPANT ADHERENCE TO TREATMENT PROTOCOL	40
g	9.3	STOPPING RULE	40
	9.4	DATA AND SAFETY MONITORING BOARD (DSMB)	40
	9.4		
9	. 5	SAFETY REVIEW PLAN	41
10	CON	NFIDENTIALITY	41
11	sou	JRCE DOCUMENTS	42
1	1.1	RECORDS RETENTION	42
12	ETH	ICAL CONSIDERATIONS	42
13	STU	DY FINANCES	
1	3.1	FUNDING SOURCE CONFLICT OF INTEREST	43
1	3.2	CONFLICT OF INTEREST.	43
1	3.3	SUBJECT STIPENDS OR PAYMENTS	43
14	REF	ERENCES	44
15	APP	ENDIX I	47

SCHEDULE OF VISITS AND PROCEDURES

	gı	(e)	(es)					
	Screening	Day 1 (Pre-Dose)	Day 1 (Post-Dose)	Week 2	Week 4	Week 6	Week 8	Week 10
Informed consent	Х							
Demographic information	Χ							
Medical history/ Con Meds/ Transplant history	Х							
Ophthalmic/ oGVHD history	Χ							
Vital signs		Х		Χ	Χ	X	Χ	Х
Best Spectacle Corrected Visual Acuity		Х						Х
Ocular Surface Disease Index (OSDI)	X	Х		Χ	Χ	X	Χ	Х
Clinical Global Impression (CGI)				Χ	Χ	Х	Χ	Х
Subject Global Assessment (SGA)				Χ	Χ	Χ	Χ	Х
Visual Analogue Scale (VAS)			Х	Х	Х	Х	Х	
Ophthalmic examination (Slit lamp)	Χ	Х		Χ	Χ	Х	Χ	Х
Schirmer 1 test and Fluorescein and Lissamine Dye staining	Х	Х					Х	
Ocular surface Redness (OR) score		Х		Χ	Χ	Χ	Χ	Х
Tear fluid analysis (PicoGreen, Cellometry)		Х					Χ	
Keratograph Oculus Redness Score		Χ			Χ		Χ	
Non-invasive Keratography Tear Film Break-up Time (NIKBUT)		Х			Χ		Χ	
Tear Meniscus Height (TMH)		Χ			Χ		Χ	
TearLab Osmolarity Test		Х			Χ		Χ	
InflammaDry for MMP-9 Protein		Х			Х		Х	
Pregnancy test (urine)*	Х							
Randomization visit		Х						
First study medication		Х						
Drug dispensation visits			Х	Х	Х	Х		
Instruction on study medication self- administration			Х	Х	Х	Х		

Version: 10.0; 07-26-2018

Physical inspection of nose & oropharynx	Х		Х	Х	Х	Х	Х
Adverse Events/ Concomitant Medications	Х	X++	Х	Х	Х	Х	Х
Conjunctival culture**	Х					Х	

^{*}If applicable ++ AEs only

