4.1 Inclusion Criteria

The PI and other members of International Chronic Ocular GVHD Consensus Group have established the consensus diagnostic criteria and classification for chronic ocular GVHD.⁴⁰

Table 1: Severity scale in chronic ocular GVHD

Severity scores (points)	Schirmer's test (mm)	CFS (points)	OSDI (points)	Conj (points)
0	>15	0	<13	None
1	11–15	<2	13–22	Mild/Moderate

Severity scores (points)	Schirmer's test (mm)	CFS (points)	OSDI (points)	Conj (points)
2	6–10	2–3	23–32	Severe
3	≤5	≥4	≥33	

CFS; corneal fluorescein staining, OSDI; Ocular Surface Disease Index. Conj; conjunctival injection. Severity classification; Total score (points); (Schirmer's test score+ CFS score+ OSDI score+ Conj injection score) = None;0–4, Mild/Moderate; 5–8, Severe, 9–11.

Table 2: Diagnosis of chronic ocular GVHD

	None (points)	Probable GVHD (points)	Definite GVHD (points)
Systemic GVHD(-)	0–5	6–7	≥8
Systemic GVHD(+)	0–3	4–5	≥6

Based on these criteria (Tables 1 and 2),⁴⁰ patients with definite ocular GVHD will be enrolled. Additionally, all of the following criteria should be met to be eligible for the study:

- Aged 18 years or older.
- Capable of giving informed consent and does provide informed consent.
- Schirmer I <10
- Corneal/ conjunctival (Fluorescein and Lissamine Dye) staining ≥1
- Ocular symptoms must be considered as annoying or activity limiting (OSDI ≥13; mild).
- Women must be post-menopausal ≥ 1 year, or surgically sterilized. If not, a negative urine pregnancy test is required within 14 days of receiving her first dose of test medication (placebo/ study drug) along with definite evidence of contraceptive use during the duration of the study. Women of reproductive age should use a method of birth control that is acceptable to the subject and the study doctor. This may include oral contraceptive pills, birth control implants, barrier methods or abstinence. If a subject mentions she suspects she may be pregnant after being enrolled, another pregnancy test will be administered. If the test is positive, she will be discontinued from the study immediately.

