6.4 Subject Enrollment

Subjects meeting the enrollment criteria (see Sections 4.1 and 4.2) will be eligible for the study.

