6.5 Study Assessments

The following detailed procedures are performed at the designated clinic visit. All results will be documented on the subject's medical/research charts, source documents, and CRFs as required. All ophthalmic procedures will be performed on both eyes.

6.5.1 Visit 1 Screening Day -18 to 0

After obtaining informed consent, the following assessments will be performed within fourteen days prior to the subject receiving the first dose of study medication:

- Demographic information including: birth date, gender, race or ethnic origin.
- Medical History including prior medication use and prior procedures: Medical history will be
 obtained by interviewing the subject and will include a history of systemic (acute or chronic)
 GVHD, stem cell transplant history (including the date and type of transplant, degree of
 mismatch, if any, etc.), allergic history (including medications and food), substance abuse history

RhDNase treatment for ocular GVHD Version: 10.0; 07-26-2018

Page 29 of 47

(including alcohol) and a history of medication use (including prescription, OTC, and herbal products) during the past 30 days will also be completed.

- Ophthalmic history including: date when the oGVHD began, verification that the subject has had definite oGVHD, medications used by the subject to treat oGVHD, previous procedures to treat oGVHD. Ocular symptoms due to oGVHD will be quantified using the Ocular Surface Disease Index (OSDI) questionnaire (section 3.3.2).
- Ophthalmic Examination (slit lamp examination, Ocular Surface Redness Score, Fluorescein and Lissamine Dye staining, and a Schirmer 1 test)
- Pregnancy test (urine), if applicable. Women of reproductive age will be asked to use a method
 of birth control that is acceptable to the subject and the study doctor. This may include oral
 contraceptive pills, birth control implants/shots or patches, barrier methods or abstinence.
 Women of reproductive age will not be included in the study if they refuse to use any birth
 control measure, including abstinence.

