Subjects currently treating oGVHD with corticosteroids and/or Restasis will continue these treatments during the whole study. If patients are wearing contact lenses (Soft bandage contact lenses or PROSE lens), they will be asked to discontinue contact lens wear for 1 month prior to being enrolled (Baseline visit) and will be required to not wear contact lenses for the duration of the study (until week 10 visit). The study doctor will provide advice about decreasing oGVHD symptoms with artificial tears, eyelid massage, or warm compresses.

If the subject agrees to enter the study, the first treatment visit will be scheduled. If a washout period is needed, visit 2 will be after 2 weeks (±4 days). If a washout period is not necessary, visit 2 can be scheduled any time in the next 2 weeks after the screening visit.

6.5.2 Visit 2 Day 1 (Randomization and First treatment visit) Prior to first dose (Baseline)

- Vital Signs (blood pressure taken while subject is relaxed in a sitting position for at least 3 minutes, pulse, temperature, and height and weight (at this visit only).
- BSCVA (Snellen's chart)
- OSDI
- Schirmer 1 test and Fluorescein and Lissamine Dye staining
- Keratograph Oculus Redness Score
 - > Non-invasive Keratography Tear Film Break-up Time (NIKBUT)
 - > Tear Meniscus Height (TMH)
- TearLab Osmolarity Test
- InflammaDry Test for MMP-9 Protein
- Baseline Ophthalmic Examination (slit lamp examination, Ocular surface redness score)
- Tear fluid collection for analysis (PicoGreen, Cellometry)
- Physical Inspection of the Nose and Oropharynx
- Conjunctival and eyelid margin cultures
- Record changes in concomitant medication
- Adverse events since screening visit.

Randomization (by pharmacy)

Investigator/designee administers first dose

Post-Dose

RhDNase treatment for ocular GVHD Version: 10.0; 07-26-2018

Page 30 of 47

- Test Substance Tolerance (Visual Analogue Scale; VAS)
- Subjects will be trained on how to self-administer the study eye drops and be given a sufficient supply to last for 2 weeks to take home.
- Subjects will receive a study diary on which to record the day/time of each dose and any adverse effects.
- Post dose evaluation for any adverse effects.

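### The washout visit window in 6.5.1 runs to 18 days after screening, but the only scheduled pregnancy test expires at 14 days and no Day 1 step prompts a repeat

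*Combined protocol and SAP*

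**What the plan says.** Two rules limit the age of the pregnancy test. For women who are neither post-menopausal nor surgically sterilized, section 4.1 says "a negative urine pregnancy test is required within 14 days of receiving her first dose of test medication", together with "definite evidence of contraceptive use during the duration of the study". Section 6.5.1 opens with a limit of the same length: "the following assessments will be performed within fourteen days prior to the subject receiving the first dose of study medication". The list that follows includes the urine pregnancy test.

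Two statements about timing run longer. The section is headed "6.5.1 Visit 1 Screening Day -18 to 0". On scheduling it says "If a washout period is needed, visit 2 will be after 2 weeks (±4 days"). Subjects who need no washout come back at any time in the 2 weeks after screening.

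In the schedule of visits, the row "Pregnancy test (urine") is marked under Screening only, where applicable. The pre-dose list for Visit 2 in 6.5.2 has no pregnancy test; randomization and the first dose follow that list. The one other route to a test is in 4.1: "If a subject mentions she suspects she may be pregnant after being enrolled, another pregnancy test will be administered". Section 6.4 ties eligibility to the criteria: "Subjects meeting the enrollment criteria (see Sections 4.1 and 4.2) will be eligible for the study".

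**The concern.** The visit window and the test limit do not fit together. A coordinator who books a washout subject inside the window and then works through the Day 1 list as written can reach the first dose with a test that 4.1 no longer accepts. Nothing on Day 1 asks how old the test is. Other screening measures (OSDI, Schirmer, staining, slit lamp) are repeated at Visit 2, so their age at screening matters less. The pregnancy test is not repeated. The retest in 4.1 depends on an enrolled subject voicing a suspicion, which has nothing to do with the age of the screening test.

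At stake is the dosing of a woman who does not meet an entry criterion and, less probably, exposure of an unrecognised pregnancy that a current test would have shown. Pregnant women are excluded under 4.2, and an exposed pregnancy brings reporting and follow-up duties under 8.5.2 and 8.6.2. Sample size, alpha and the efficacy analysis are not involved.

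**Working it through.** **Inputs**
- Visit 2 with washout: 2 weeks ± 4 days after screening (6.5.1).
- Visit 2 without washout: within 2 weeks of screening (6.5.1).
- Maximum age of the test at first dose: 14 days (4.1 and the opening of 6.5.1).
- Scheduled tests: one, at screening (schedule table; 6.5.1; absent from 6.5.2).
- First dose: at Visit 2 (6.5.2).

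**Reproducing the plan's own figure.** The window is 14 − 4 = 10 to 14 + 4 = 18 days. The upper end agrees with the Day −18 in the heading of 6.5.1. If Day 0 is counted as a calendar day, Day −18 to a Day 1 dose is 1 − (−18) = 19 days; without a Day 0 it is 18. I use the visit window, which gives 18 directly.

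**Days in the window.** 18 − 10 + 1 = 9.

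**Days beyond the limit.** Days 15, 16, 17 and 18, which is 4 of 9. The overrun is from 15 − 14 = 1 day to 18 − 14 = 4 days.

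**No washout.** The interval is at most 14 days, so the overrun is 0.

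**After a repeat test on Day 1 whenever the screening test is over 14 days old.** The test is 0 days old at dosing on days 15 to 18 and at most 14 days old on days 10 to 14, so 0 of 9 days breach the limit. Capping the washout visit at 14 days would also work (days 10 to 14, 0 of 5 in breach), but it gives up the upper half of the scheduling tolerance.

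**The case against.** The strongest reply is that the protocol already forbids the breach. The 14-day limit is stated twice, eligibility depends on 4.1, and a scheduling tolerance waives no entry criterion. Read together, the sections let a woman who needs the test be dosed on days 10 to 14, or later with a newer test. That stands. A reader might infer that 6.5.1 authorises dosing on an expired test, and the documents do not support that. What is missing is a step that reconciles the two rules, not the requirement itself.

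A second reply is that the test could be done on a later day of the screening period, inside 14 days of dosing, which would satisfy every sentence. The text does not rule this out. But it describes screening as Visit 1 and times Visit 2 from the screening visit, and nothing tells staff to delay the test or bring the subject back for it.

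A third reply points to other controls. Section 9.1.1 has the PI or staff review all data forms continuously, including for protocol compliance, and 8.10 requires staff training on the protocol. It would be wrong to infer that the semiannual review of entry criteria in 9.2.1 is the only safeguard. Neither control, however, is tied to a check before the first dose.

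Finally, the consequence is small. A test up to 14 days old is acceptable by design, evidence of contraception is mandatory, and women who refuse birth control are not enrolled. This lowers the chance of an undetected pregnancy; it does not renew the test.

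**Conclusion.** The inconsistency is real and minor. On 4 of the 9 days in the washout window the screening pregnancy test is 1 to 4 days past the limit, and no scheduled procedure prompts the repeat. The breach is possible, not certain.

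The size needs care on two counts. First, 4 of 9 is a share of calendar days. A reader might take it as a share of subjects, but the documents do not say how many women of childbearing potential need a lens washout, nor how visits will spread over the window. In a trial of 72 the number affected is probably small and could be zero.

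Second, a reader might infer a much larger overrun from the rule in 4.2, 5.6 and 6.5.1 that lenses be stopped 1 month before baseline. If lenses stopped at screening and a month is taken as 28 to 31 days, the test would be 28 − 14 = 14 to 31 − 14 = 17 days too old. But such a visit falls outside the 18-day window, so 6.5.1 does not allow it to be scheduled. That figure belongs to a separate conflict, between the 14-day washout in 1.5 and the 1-month rule, and is no measure of this point. If the 1-month rule is followed, days 15 to 18 are reached only by women who had stopped lenses before screening.

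The conclusion assumes that the test is done at the screening visit, as the schedule and 6.5.1 indicate, and that staff add no unscheduled test.

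**What to change.** In 6.5.2, add to the pre-dose list, ahead of randomization: *urine pregnancy test (if applicable), negative before randomization and first dose, if the screening test is more than 14 days old*. Add the matching conditional entry under Day 1 (pre-dose) in the schedule table. Leave the 14-day limits in 4.1 and 6.5.1 as they are; the visit window can also stay.

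The cost is two protocol entries and one extra urine test for each woman whose screening test has passed 14 days at Visit 2. The change closes the pregnancy-test gap only. The differing washout lengths, and the fourteen-day rule for the other screening assessments, need their own correction.

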6.5.3 Visit 3: Week 2 (± 2 days)

Treatment Visit (after any dose for that day)

- Vital Signs
- OSDI
- Clinical Global Impression, Subject Global Assessment
- Test Substance Tolerance (VAS)
- Ophthalmic Examination (slit lamp examination, Ocular surface redness score)
- Physical Inspection of the Nose and Oropharynx
- Review the subject's diary and record changes in concomitant medication, deviations from drug schedule and adverse events.
- Subjects will be given study medication, sufficient to last for 2 weeks, to take home.

6.5.4 Visit 4: Week 4 (± 2 days)

Treatment Visit (after any dose for that day)

- Vital Signs
- OSDI
- Keratograph Oculus Redness Score
 - > Non-invasive Keratography Tear Film Break-up Time (NIKBUT)
 - > Tear Meniscus Height (TMH)
- TearLab Osmolarity Test
- InflammaDry Test for MMP-9 Protein
- Clinical Global Impression, Subject Global Assessment
- Test Substance Tolerance (VAS)
- Ophthalmic Examination (slit lamp examination, Ocular surface redness score)
- Physical Inspection of the Nose and Oropharynx
- Review the subject's diary and record changes in concomitant medication, deviations from drug schedule and adverse events.
- Subjects will be given study medication, sufficient to last for 2 weeks, to take home.

6.5.5 Visit 5: Week 6 (± 2 days)

Treatment Visit (after any dose for that day)

- Vital Signs
- OSDI
- Clinical Global Impression, Subject Global Assessment
- Test Substance Tolerance (VAS)
- Ophthalmic Examination (slit lamp examination, Ocular surface redness score)
- Physical Inspection of the Nose and Oropharvnx

- Review the subject's diary and record changes in concomitant medication, deviations from drug schedule and adverse events.
- Subjects will be given study medications, sufficient to last for 2 weeks, to take home.

6.5.6 Visit 6: Week 8 (± 2 days)

Treatment Visit (after any dose for that day)

- Vital Signs
- OSDI
- Fluorescein and Lissamine Dye staining, and Schirmer 1 test
- Keratograph Oculus Redness Score
 - > Non-invasive Keratography Tear Film Break-up Time (NIKBUT)
 - > Tear Meniscus Height (TMH)
- TearLab Osmolarity Test
- InflammaDry Test for MMP-9 Protein
- Clinical Global Impression, Subject Global Assessment
- Test Substance Tolerance (VAS)
- Ophthalmic Examination (slit lamp examination, Ocular surface redness score)
- Tear fluid collection for analysis (PicoGreen, Cellometry)
- Physical Inspection of the Nose and Oropharynx
- Conjunctival and eyelid margin cultures
- Review the subject's diary and record changes in concomitant medication, deviations from drug schedule and adverse events.

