1.5 Dose Rationale and Risk/Benefits

RhDNase I 1mg/ml (0.1%) will be applied topically to the ocular surface as eye drops. This is the same dose as is currently in use in patients with Cystic Fibrosis. The drug formulation is being used unchanged. This dose has been effective in reducing eDNA content when given to patients with cystic fibrosis. We do not expect any serious adverse events with this dose.

Drugs are routinely applied topically to the ocular surface as eye drops because of easy access to the ocular tissues and good drug bioavailability. Therefore, we will use rhDNase I topically. Since rhDNase I does not accumulate in tissues and its enzymatic activity is expected to be short-lived, we have elected to use the eye drops four times a day. The ocular residence time for emulsion eye drops (e.g. Restasis, used twice a day) has been estimated as approximately 2 hours.³³ We expect even shorter ocular residence time for rhDNase I, given the lower viscosity of its vehicle. Future clinical trials will be needed to assess whether lower frequency of dosing is also effective. The feasibility of performing this trial would have been suspect if we had included more than one dosing in this trial because of the much larger number of oGVHD patients needed.

Since rhDNase I is not expected to increase the production of natural DNase I, but rather it only supplements it so that the imbalance of decreased tear fluid DNase I is corrected, we expect long-term use of rhDNase I. Thus, we have chosen an eight weeks duration of therapy as it will give us better data to predict side effects during long-term use.

RhDNase I is currently used as an inhaled drug in adults and children with cystic fibrosis. Patients with cystic fibrosis have experienced a change in or loss of their voice, discomfort in the throat, chest pain, red watery eyes, rash, dizziness, fever, or runny nose. Most of these are systemic side-effects that are not generally seen with eye drops. These side effects are usually mild and short-lived.

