3.3.9 Tolerability End Point: Test Substance Tolerance (Visual Analogue Scale)

Subjects will assess their tolerance to the administration of the test medication (placebo/ study drug), utilizing a Visual Analog Scale (VAS). The VAS is a 100 mm horizontal line with verbal descriptors at either end. The VAS ratings will be completed after administration of the test medication on Day 1 (post-dose), week 2, week 4, week 6 and week 8. Subjects will place a single slash mark across the horizontal line between the end labeled "completely intolerable" (0 mm) and "easily tolerable" (100mm). The VAS rating is as follows:

Please rate the degree of comfort or lack of comfort associated with administering the eye drop by making one slash mark on the line below:

Visual Analogue Scale

On the scale of 0 to 100 seen below, please mark where you would rate your tolerability to administration of the test drug.

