7.1 Sample Size Determination

The sample size is based on the primary efficacy end point (corneal RBS score) using the following assumptions: (i) mean RBS score in ocular GVHD population = 3.1, (ii) sigma (standard deviation) = 2.5, (iii) expected mean based on 60% effect = 1.24. These assumptions are based on our preliminary data in ocular GVHD patients where we found that treatment with DNase I eye drops reduced RBS score by 80% (mean).²⁵ A total of 30 subjects in each group will be required to detect the difference between groups using a 2-sided two-sample t test with an alpha level of 0.05 and 80% power. We elected to enroll 36 subjects per group.

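### Tear and ocular tests on treatment, and the tolerability VAS, are taken at an uncontrolled time after a drop, so week 8 eDNA cannot separate a transient post-dose effect from sustained clearance

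*Combined protocol and SAP*

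**What the plan says.** Section 6.5.2 lists the Day 1 tests under a heading that reads "Randomization and First treatment visit) Prior to first dose (Baseline". The list includes dye staining, Schirmer, the Keratograph measures, TearLab osmolarity, InflammaDry and tear collection. Sections 6.5.3 to 6.5.6 (weeks 2, 4, 6 and 8) each open with "Treatment Visit (after any dose for that day". Section 5.2 places the drops at about 8 a.m., noon, 4 p.m. and 8 p.m. No minimum, maximum or target time since the last drop appears in those visit sections, in the device sections (3.3.6 to 3.3.8) or in the tear-sampling section (3.4.3).

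- Tear eDNA and the Schirmer strip are taken on treatment at week 8 only.
- Keratograph redness, NIKBUT, tear meniscus height (TMH), osmolarity and MMP-9 are taken at weeks 4 and 8.
- The off-drug week 10 visit (6.5.7) repeats none of these.

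Section 1.5 says the residence time of an emulsion drop "has been estimated as approximately 2 hours" and expects a shorter time for the study drug, without a figure.

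Section 3.2 makes the change in tolerance from Day 1 post-dose to weeks 2, 4, 6 and 8 the primary tolerability endpoint. Section 3.3.9 says: "The VAS ratings will be completed after administration of the test medication on Day 1 (post-dose", and then lists the later visits. The investigator gives the first dose in clinic (1.5, 6.5.2). Later doses are self-given at home (5.1).

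Section 7.2 compares every outcome between arms with treatment, time and their interaction in the model. Section 5.5 has subjects write study-dose times in a diary.

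**The concern.** The baseline state contains no study drop. The on-treatment state may or may not, depending on when the subject dosed and when the appointment fell. This matters in three ways.

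**eDNA.** Clearing eDNA from the tear film is the trial's rationale (1.3). If residual enzyme is in the tear film or in the collected sample at week 8, measured eDNA can be low because a drop was recent. Only the active arm can carry that residue, so the vehicle arm does not cancel it. Week 10 gives no off-drug eDNA value to settle the question.

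**Fluid-sensitive tests.** Residual fluid can change osmolarity, TMH and NIKBUT readings against a baseline free of study drop. Variable timing adds scatter.

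**VAS.** The question concerns comfort when administering the drop. The reference rating and the later ratings are made in different settings and at different delays, so change over time mixes drug tolerance with setting and recall.

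**Working it through.** **1. The plan's own figure.** Section 7.1 gives "mean RBS score in ocular GVHD population = 3.1", "sigma (standard deviation) = 2.5" and "expected mean based on 60% effect = 1.24", and sizes the trial "using a 2-sided two-sample t test with an alpha level of 0.05 and 80% power".

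- Difference: 3.1 − 1.24 = 1.86, which is 60% of 3.1.
- Normal approximation: n = 2 × (1.960 + 0.842)² × 2.5² / 1.86² = 28.4, so 29 per group.
- Exact t test: 29.35, so 30 per group, as stated. Power is 80.9% at 30 and 87.6% at the planned 36.

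Measurement timing enters none of these inputs, so the sample size stands.

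**2. How much the interval can vary.** With drops every 4 hours from 8 a.m., time since the last drop runs from minutes to about 4 hours. Assume visit times spread evenly from 9 a.m. to 5 p.m.:

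- within 2 h of a drop: 9–10, 12–2 and 4–5 o'clock, 4 of 8 hours = 50%
- within 1 h: 12–1 and 4–5 o'clock, 2 of 8 = 25%
- within 30 min: 1 of 8 = 12.5%

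Starting at 8 a.m. instead gives 56%, 33% and 17%.

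**3. How much enzyme could remain.** The drop is 1 mg/mL = 1,000,000 ng/mL (1.5). Normal tear DNase I is 3.14 ng/mL (1.3). Ratio: 1,000,000 / 3.14 = 318,471. Halvings needed to reach normal: log2(318,471) = 18.3.

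Assuming first-order loss, the longest half-life that returns the level to normal is t / log2(ratio / dilution):

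| Assumed dilution at instillation | Normal by 2 h | Normal by 4 h |
|---|---|---|
| none | 120 / 18.3 = 6.6 min | 240 / 18.3 = 13.1 min |
| 10-fold | 120 / 15.0 = 8.0 min | 240 / 15.0 = 16.0 min |
| 100-fold | 120 / 11.6 = 10.3 min | 240 / 11.6 = 20.6 min |

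The documents give no tear half-life. Without dilution, the level as a multiple of normal is 318,471 × 0.5^(t / half-life):

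| Assumed half-life | 1 h | 2 h | 4 h |
|---|---|---|---|
| 5 min | 78 | 0.02 | about 0 |
| 10 min | 4,976 | 78 | 0.02 |
| 20 min | 39,809 | 4,976 | 78 |
| 60 min | 159,236 | 79,618 | 19,904 |

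The same drop can leave thousands of times the normal level or almost none, depending on an interval the plan leaves open and a half-life it does not give.

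**4. Which contrasts are exposed.**

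- *eDNA abundance and strand length (secondary endpoints 17 and 19):* enzyme is in one arm only, so the between-arm comparison at week 8 is exposed.
- *Osmolarity, TMH, NIKBUT:* the vehicle has the same ingredients without the enzyme (5.1), on the same schedule (5.2). The fluid effect falls on both arms. Within-arm change and variance are affected.
- *VAS:* both arms share the mismatch between clinic and home ratings. Within-arm change is affected.

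**The case against.** A reader might infer that residual drop fluid can pass for a treatment effect across the tear-film measures. The documents do not support this. The control is a matched vehicle on the same schedule, and section 7.2 compares arms, so a fluid effect is balanced by randomization. Nor do they show that fluid hides a real osmolarity difference. Simple mixing with a fraction f of drop fluid in both arms would shrink a true difference to (1 − f) of its size, but the documents give neither f nor a tear osmolarity.

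A reader might also infer that the primary efficacy endpoint is compromised. No mechanism or figure in the documents shows an effect on corneal staining.

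For eDNA the opposing case is stronger than it first looks:

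- Digesting DNA on the eye is the drug's intended action, so lower eDNA soon after a drop is not in itself false. What remains is whether the effect is transient or sustained.
- Digestion in the collected sample is possible but unproven. Section 3.4.3 refers to a publication for the assay, and any step that stops enzyme activity may be described there.
- Diaries record study-dose times, so the interval may be recoverable. But no section carries it to the test record or the model, and for artificial tears section 5.6 asks only for number of drops and frequency.
- Baseline is free of study drops only. Other eye treatments continue, with no stated interval before any visit.

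On the VAS, section 3.3.9 does place every rating after administration, Day 1 included, and the delay on Day 1 is not stated either. Section 5.4 has the subject demonstrate instillation in the other eye before staff, so the contrast in who gives the drop may be less sharp. The difference in setting and the unspecified delay at weeks 2 to 8 remain.

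Finally, sampling just before the next drop may not remove all enzyme: without dilution, that needs a half-life of 13.1 minutes or less.

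**Conclusion.** The point holds in limited scope and is worth correcting.

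- **Week 8 eDNA abundance and strand length:** a transient post-dose effect, or a possible in-sample one, cannot be separated from sustained clearance, because residual enzyme can exist in the active arm only. The size is unknown. Under the assumed half-lives of 5 to 60 minutes (first-order loss, no dilution), the 2-hour level runs from 0.02 to about 80,000 times normal. These are secondary endpoints, but they carry the trial's mechanism.
- **Osmolarity, TMH, NIKBUT:** added noise and distorted change from baseline within each arm, not a false between-arm effect. Not quantifiable from the documents.
- **Primary tolerability VAS:** within-arm change from Day 1 is distorted, with both arms affected alike. Not quantifiable from the documents.
- **Corneal staining and sample size:** no effect shown. The stated 30 per group reproduces.

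Appendix I was not in the text reviewed, so any timing rule there could not be checked.

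**What to change.** 1. In 6.5.4 and 6.5.6, replace the open rule for ocular measurements and tear samples with one fixed point in the existing dosing interval, preferably just before the next scheduled drop.
2. Record on the CRF the time since the last study drop and the last artificial tear for each test.
3. In 7.2, add a sensitivity analysis of week 8 eDNA using time since the last study drop, allowing its relation to differ by arm. The interval is not randomized, so treat the result as supportive.
4. In 3.4.3, state how enzyme activity in collected tears is handled before the assay. End-of-interval sampling alone may not remove it.
5. In 3.3.9 and 6.5.2 to 6.5.6, rate the VAS at the same defined time after a drop at every visit, using a dose already scheduled for that time. Reconcile this with the home self-administration statement in 5.1.

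The number and timing of doses do not change. The cost is protocol and CRF wording, a supervised drop with a timed rating at the treatment visits, and less freedom in booking appointments. A week 8 sample taken at an uncontrolled time cannot be repeated later.
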